Study Protocol and Statistical Analysis Plan

Study Title: Impacts of Clinician-Mediated Report-Back

NCT number: NCT06074159

Document date: January 30, 2026

Study design overview

We collaborated with two prospective pregnancy cohort studies, Puerto Rico Testsite for Exploring Contamination Threats (PROTECT) and Environmental Reproductive and Glucose Outcomes (ERGO), to report-back exposure results to participants. PROTECT is based in the northern karst region of Puerto Rico, an area with significant historical pollution, and is investigating the contribution of environmental contamination to adverse pregnancy outcomes such as pre-term birth. Participants are recruited from partnered community health clinics during early pregnancy. ERGO is based in Boston, Massachusetts, and studies the impact of environmental exposures from personal care products on maternal and child cardiometabolic health outcomes such as postpartum glucose intolerance. ERGO recruits participants from two Harvard teaching hospitals, Brigham and Women's Hospital and Israel Deaconess Medical Center, during prenatal visits. For both cohorts, participants provided urine samples during pregnancy and/or at postpartum. Samples were measured for phenolic compounds (parabens, antimicrobials, dichlorophenols, UV filters, and bisphenols) in PROTECT and phthalates in both cohorts.

The present study evaluated the impact of self-guided versus clinician-guided report-back. For both cohorts, participants were randomly assigned to the clinician-guided or self-guided intervention group. One ERGO participant was prospectively assigned to the clinician-guided group to ensure that all clinicians participated in ≥ 2 report-back visits with participants and increase the number of eligible participant interviewees.

Participants were contacted by phone, email, and/or text message for recruitment into the study. In ERGO, all participants were contacted by the ERGO study coordinator. In PROTECT, eligible participants randomly assigned to the clinician-guided group were contacted by a study-affiliated nurse who scheduled their in-clinic report-back appointment, while those assigned to the self-guided group were contacted by other study coordinators.

Following recruitment, participants in both groups completed baseline surveys. Participants assigned to the self-guided report-back group received an access code to view their report online, while those assigned to clinician-guided report-back were scheduled for an appointment to meet with a clinician in-person at a clinic (PROTECT) or virtually (ERGO). Because clinician involvement in environmental health report-back is novel, we recruited a subset of participants in the clinician-guided report-back group for semi-structured interviews to learn about their experiences in greater depth.

All study protocols were reviewed and approved by the institutional review boards at Harvard University and the University of Puerto

Digital Reports

Personal exposure reports were developed collaboratively by Silent Spring Institute and members of the cohort study teams using the Digital Exposure Report-Back Interface (DERBI) (Boronow et al. 2017). Reports could be viewed from desktop computers, tablets, and smartphones using a unique access code. Reports included participants' individual measurement results reported in text and displayed in graphs with comparisons to other study participants and to a representative sample of reproductive-aged women in the U.S. as calculated from the National Health and Nutrition Examination Survey (NHANES). Alongside individual results, reports included contextual information about chemical sources, associated health effects, and recommended ways to reduce exposure. Each report also included information about overall study results, suggested community actions, and a list of common questions and contact information for the study teams. An example PROTECT report can be viewed online (<https://protect-es.reportback.org/r/report/demo>).

Clinician involvement

We recruited 9 clinicians to report back exposure results to participants using DERBI. In PROTECT, all recruited clinicians (n = 6) were PROTECT-affiliated nurses who have supported research activities, including participant recruitment, sample collection, and administration of questionnaires. PROTECT nurses attended two in-person training sessions during which study staff provided information about the sources and health impacts of the chemicals included in the report and instructions for navigating the DERBI platform. Following a mock report-back demonstration, nurses practiced discussing participant results and answering common questions.

While our team initially intended to engage clinicians who were part of the ERGO study, due to significant staff turnover at participating hospitals (Brigham and Women's Hospital and Israel Deaconess Medical Center), we instead independently recruited clinicians with no connection to ERGO through existing networks, including direct invitations and advertisements over medical listservs. For ERGO report-back, clinicians (n=3) had no previous affiliation with the ERGO study and included one physician assistant, one genetic counselor, and one pediatric physician. Training sessions for clinicians returning results to ERGO participants took place over two virtual sessions totaling two hours and 30 minutes, and included the same components as the PROTECT training. In addition, as clinicians sharing results with ERGO participants had no previous experience with the study and requested additional support, they received a script to use during the report-back session.

Clinicians met with participants assigned to the clinician-guided report-back group in brief (20-30 minutes), one-on-one appointments. In PROTECT, participants travelled to study-

affiliated community health clinics to review their online reports with a clinician, whereas ERGO appointments took place virtually through Zoom and clinicians shared their screen. At the end of the appointment, participants were given the access code to log into their reports so they could revisit them independently. Participants assigned to the self-guided group logged into their online reports independently and did not review their results alongside a clinician or other research staff.

Pre- and post-surveys

Participants completed a 15-minute pre-survey at baseline and a 20-minute post-survey at least two weeks after accessing their reports. Surveys were comprised of a series of questions across domains, including feelings, satisfaction, perceived self-efficacy, knowledge, exposure behaviors, and, for PROTECT only, study relationships.

For the feelings section, using a six-point Likert-scale (from “Not at all” to “Very Strong”), participants rated how strongly they experienced feeling respected, empowered, worried, and (post-survey only) surprised in relation to report-back. Satisfaction was assessed in the post-survey across four questions using a 5-point Likert scale from “Strongly disagree” to “Strongly agree.” In the knowledge section, participants were asked to answer whether a series of statements were “True”, “Probably true”, “Probably false”, or “False.” The knowledge section contained 9 questions in ERGO and for PROTECT, two additional knowledge questions relevant to compounds included in PROTECT reports. The perceived self-efficacy section asked participants to rate their confidence across seven different statements using a seven-point scale from “Cannot do it at all” to “Highly certain I can do it.” In the exposure behaviors section, participants rated how frequently they performed certain actions using a four-point scale from “never” to “almost every day” or from “never” to always.” The post-survey behavior section also included yes/no questions about changes made after receiving reports and open-ended questions for further elaboration. In PROTECT, pre- and post-surveys also included a set of questions asking about relationships to clinical care and the PROTECT study, which participants answered on a five-point scale from “strongly disagree” to “strongly agree.” For each question, participants also had the option to select “Don’t Know” or “Decline to Answer.” Full survey instruments can be found in supplemental material.

Based on the preferences of partnering study teams for participant communications, PROTECT participants completed pre- and post-surveys over the phone with a study staff member or PROTECT-affiliated nurse who was not involved directly in reporting back results to participants, while ERGO participants completed surveys online in REDCap, a web application for building and managing surveys.

Survey Analysis

All data analysis was restricted to participants who completed the pre- and post-surveys and viewed their DERBI reports. We first conducted stratified analyses to summarize participant responses across domains and characterize changes before and after report-back. For each cohort and intervention group, we calculated descriptive statistics on pre- and post-survey responses. To assess pre- and post-survey changes over time, we used Wilcoxon signed-rank tests with the Pratt method. For the knowledge section, true/probably true and false/probably false questions were re-coded to indicate correctness, and McNemar's tests were conducted to assess changes in item-level responses.

To further explore the impact of the interventions, we used multiple regression to model survey responses of both cohorts and intervention groups (clinician-guided and self-guided). Our main model was a linear mixed effects model that included intervention group, cohort, and survey timepoint as predictors and an interaction between survey time point and intervention group. We also included a random intercept for each participant. Report-back group and cohort were factorized with the online-only group and the PROTECT cohort as reference levels.

Self-efficacy was modeled as a scale by summing responses across all self-efficacy questions for each participant at the pre- and post-survey. Internal consistency of the self-efficacy scale was evaluated using Cronbach's alpha. Knowledge was modeled as an index, and we summed the number of correct responses and normalized to the number of questions included in the survey (11 questions in PROTECT and 9 in ERGO). For binary yes/no behavior changes, we used an analogous logit link function. For post-survey-only outcomes (the feeling "surprised", satisfaction, and behavior changes), we used multiple regression models that included fixed effects for intervention group and cohort only (no random effect).

To evaluate the robustness of these models, sensitivity analyses were conducted by comparing our main regression models with alternate models. Model performance was compared using Akaike Information Criterion (AIC) and we report model effect estimates and confidence intervals for key predictors. All analyses were conducted using R version 4.1.1 using the `lm()` and `lmer()` functions from the `stats` and `lme4` packages, respectively.

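### The between-group models have no rule for the one ERGO participant who was placed in the clinician-guided group without randomisation

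*Combined protocol and SAP*

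**What the plan says.** On allocation, the Study design overview states: "For both cohorts, participants were randomly assigned to the clinician-guided or self-guided intervention group". It follows at once with the exception: "One ERGO participant was prospectively assigned to the clinician-guided group to ensure that all clinicians participated in" at least two "report-back visits with participants and increase the number of eligible participant interviewees". Neither the allocation ratio nor the method of randomisation is given.

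On who is analysed, Survey Analysis states: "All data analysis was restricted to participants who completed the pre- and post-surveys and viewed their DERBI reports". Having been randomised is not a condition.

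On the comparison, Survey Analysis states: "Our main model was a linear mixed effects model that included intervention group, cohort, and survey timepoint as predictors". It adds a time-by-group interaction and a random intercept per participant. Outcomes collected only after report-back (surprise, satisfaction, behaviour changes) are modelled on group and cohort alone. On robustness, it says that "sensitivity analyses were conducted by comparing our main regression models with alternate models", judged by AIC. No alternate analysis population is named.

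**The concern.** The study sets out to compare self-guided with clinician-guided report-back, and what supports a causal reading of that comparison is random allocation. One person in the clinician-guided group had no chance of being in the other group. The assignment could only add to one side, so no matching self-guided record offsets it. Nothing in the analysis section flags, excludes or sets aside this record.

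The post-survey-only models are the most exposed. They contain no baseline measure, so comparability of the groups rests on randomisation alone. The mixed models at least compare each person's change from their own starting point.

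At stake is whether the between-group estimates can be described without qualification as a randomised comparison. The likely numerical disturbance is a lesser matter.

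**Working it through.** The documents state no sample size, power or effect size, so there is no figure of the plan's own to reproduce. The check has two parts.

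**Does any rule remove this person?**

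- Allocation: one ERGO participant was placed in the clinician-guided group for a purpose that only that group could serve. This is not a random assignment.
- Analysis filter: pre-survey done, post-survey done, report viewed. None of the three depends on how the person was allocated.
- Models: group, cohort, timepoint and time-by-group in the mixed model; group and cohort in the post-only models. There is no term for this record.
- Sensitivity analyses: different models, with no different population.

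So no rule removes the person. Whether they completed both surveys and viewed the report is not stated, and entry into the models is therefore conditional on that.

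**How much could one record matter?**

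The relevant estimate pools the cohorts. Cohort does not interact with time, so with complete pre/post responses the time-by-group term is the difference in mean change between the pooled groups. The post-only group term behaves the same way if the allocation ratio is similar in the two cohorts (an assumption).

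Floor on the pooled clinician-guided arm: the quota covers all clinicians, and Clinician involvement gives 9 of them (6 PROTECT, 3 ERGO). 9 × 2 = 18 visits. Treating each visit as one analysed participant is an assumption.

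With n analysed in that arm:

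- share of the arm = 1/n
- shift in the arm mean from a person who differs from the rest by d = d/n
- standard error of a simple 1:1 difference with SD 1 = √(2/n), so a 2 SD deviation shifts the estimate by (2/n)/√(2/n) = √(2/n) standard errors

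The deviations of 2 points and 2 SD are illustrative and have no source in the documents.

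| n (assumed) | Share | Shift for 2 points | Shift for 2 SD, in standard errors |
|---|---|---|---|
| 18 | 5.6% | 0.11 | 0.33 |
| 30 | 3.3% | 0.07 | 0.26 |
| 50 | 2.0% | 0.04 | 0.20 |
| 100 | 1.0% | 0.02 | 0.14 |

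**The case against.** The best defence is that this is one openly disclosed person. The exception and its reason stand directly after the randomisation statement, so no reader is misled about allocation. The models are introduced as further exploration, with no primary hypothesis or significance level stated. Even a 2 SD outlier moves the estimate by about a third of a standard error at the assumed floor, and nothing shows that a conclusion would change. Keeping the person and adding a randomised-only sensitivity analysis would also answer the point.

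Most of this stands, and it limits the severity. It does not settle how the record is to be analysed: disclosing an exception in the design section is not a rule in the analysis section.

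A reader might also infer more than the documents support:

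- *That an ERGO randomised contrast is distorted.* The quote "For ERGO report-back, clinicians (n=3) had no previous affiliation with the ERGO study" gives 3 clinicians, hence a floor of 3 × 2 = 6 visits, a share of 1/6 = 17% and a 2-point shift of 2/6 = 0.33. That figure applies to the ERGO clinician-guided mean. Survey Analysis plans no ERGO between-group test, and the main model has no cohort-by-group term.
- *That the cohort-level tests are invalid.* The Wilcoxon signed-rank and McNemar tests compare before with after inside each cohort and group. They do not rest on randomisation.
- *That the person was chosen for willingness.* Only operational reasons are given. How this individual was selected is not stated.
- *That ERGO, or its clinician-guided arm, is small.* No arm sizes are given. Fewer clinicians does not mean fewer participants, and uneven scheduling could equally leave one clinician short of two visits.

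**Conclusion.** The gap is real but modest. As written, the plan would carry a non-randomised record into the pooled mixed models and the post-survey-only models, provided that this person completed both surveys and viewed the report. The disturbance is at most about 5.6% of the pooled clinician-guided arm, or about 0.11 points for a 2-point deviation. Those ceilings depend on there being at least 18 analysed clinician-guided participants. They fall as the arm grows, and would be higher if fewer than 18 people who attended visits completed the study.

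The case for acting rests on validity at almost no cost. A comparison presented as randomised should contain only randomised participants, or should show what happens without the exception. This is a should-fix point. The documents do not support treating it as a threat to the study's conclusions.

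**What to change.** Add one rule to Survey Analysis: the between-group models (the linear mixed models and the linear and logistic post-survey-only models) include randomised participants only, and the same models with the non-randomised ERGO participant added are reported as a sensitivity check.

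Keep this person in the interviews, the descriptive summaries and the pre/post tests within the ERGO clinician-guided group. A footnote there should give the manner of assignment and say whether the person met the completion and viewing conditions.

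The cost is one sentence of text, one fewer observation in the comparative models, and a refit if those models have already been run.

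### For outcomes in both surveys, the main model's arm contrast is an unadjusted difference in mean change: valid under randomisation, but less precise than one adjusted for pre-survey score and cohort

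*Combined protocol and SAP*

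**What the plan says.** The Survey Analysis section describes one main model for outcomes measured before and after report-back: "Our main model was a linear mixed effects model that included intervention group, cohort, and survey timepoint as predictors", together with "an interaction between survey time point and intervention group". On the random part it says: "We also included a random intercept for each participant". The analysis set is narrow: "All data analysis was restricted to participants who completed the pre- and post-surveys and viewed their DERBI reports". There are exactly two time points: "Participants completed a 15-minute pre-survey at baseline and a 20-minute post-survey at least two weeks after accessing their reports". Allocation is described in the Study design overview: "For both cohorts, participants were randomly assigned to the clinician-guided or self-guided intervention group", with a single exception: "One ERGO participant was prospectively assigned to the clinician-guided group".

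The document does not say which coefficient is the arm effect, but the interaction is the only term that compares change between arms. No baseline-adjusted model is named. The sensitivity models are described only as alternates, compared by AIC.

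The point applies to outcomes with a value in both surveys: three of the feelings items, the self-efficacy scale, the knowledge index, the behaviour frequencies and, in PROTECT, the study-relationship items. It does not apply to post-survey-only outcomes such as surprise, as the feelings description shows: "participants rated how strongly they experienced feeling respected, empowered, worried, and (post-survey only) surprised in relation to report-back".

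**The concern.** In this model the pre-survey score is an outcome, not a covariate. With two time points and a free group main effect, the arm contrast becomes post minus pre in one arm against post minus pre in the other, which fixes the coefficient of the pre-survey score at 1. Unless pre and post are very highly correlated, that coefficient is too large and adds noise.

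Listing cohort as a predictor also suggests that the contrast is cohort-adjusted, and it is not. This matters because the cohorts differ in setting, survey mode, appointment format, type of clinician and number of knowledge items.

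At stake are wider confidence intervals than the collected data require, and an estimate that moves with chance baseline differences between arms.

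**Working it through.** The document states no sample size, SD, pre/post correlation or power, so there is no figure of its own to reproduce. The model structure and the two time points come from the document. Every rho, effect size and sample size below is an assumption.

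**1. What the interaction estimates.** Let g be group, c cohort and u the participant intercept, with time coded 0 and 1. Splitting each complete pair into its change and its mean:

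- change = b_time + b_int·g + (e_post − e_pre)
- mean = b_0 + b_group·g + b_cohort·c + (b_time + b_int·g)/2 + u + mean error

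Cohort and u do not appear in the change. In the mean, the free b_group absorbs b_int/2, so b_int is identified by the changes alone. It is therefore the difference in mean change, not adjusted for cohort.

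Three simulated data sets of 60 participants in two arms and two cohorts, all pairs complete, confirm this:

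| rho | Mixed-model interaction (SE) | Raw difference in change (SE) | Change adjusted for cohort | ANCOVA (SE) |
|---|---|---|---|---|
| 0.3 | 0.1328 (0.2752) | 0.1328 (0.2752) | 0.0872 | −0.0064 (0.2310) |
| 0.5 | 0.5932 (0.2222) | 0.5932 (0.2222) | 0.5907 | 0.5476 (0.1933) |
| 0.7 | 0.2715 (0.2319) | 0.2715 (0.2319) | 0.2935 | 0.3427 (0.2223) |

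The second and third columns agree; the fourth differs, so the stated interaction carries no cohort adjustment. If the random-intercept variance is estimated as zero, the point estimate is unchanged but the SE differs. Where an item has unpaired answers, the equality is close rather than exact.

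**2. Precision.** With common SD s, the per-participant variances behind the two contrasts are:

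- change score: 2s²(1−rho)
- ANCOVA: s²(1−rho²)
- ratio: (1−rho)(1+rho) / [2(1−rho)] = (1+rho)/2

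The last two columns assume an effect of 0.5 SD, two-sided alpha 0.05, and change score versus ANCOVA.

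| rho (assumed) | Ratio | Variance saved | Equivalent extra participants (1/ratio − 1) | n per arm for 80% power | Power at 50 per arm |
|---|---|---|---|---|---|
| 0.3 | 0.65 | 35% | 54% | 88 vs 58 | 0.56 vs 0.75 |
| 0.5 | 0.75 | 25% | 33% | 63 vs 48 | 0.71 vs 0.82 |
| 0.7 | 0.85 | 15% | 18% | 38 vs 33 | 0.90 vs 0.94 |
| 0.9 | 0.95 | 5% | 5% | 13 vs 12 | both about 1.0 |

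With unequal SDs, the change-score variance minus the ANCOVA variance is (s_pre − rho·s_post)². This is never negative, so ANCOVA is at least as precise in large samples.

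In 6,000 replicates per setting, the empirical SEs (change score vs ANCOVA) were:

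| Per arm | rho 0.3 | rho 0.5 | rho 0.7 |
|---|---|---|---|
| 20 | 0.371 vs 0.306 | 0.316 vs 0.282 | 0.244 vs 0.232 |
| 50 | 0.236 vs 0.193 | 0.201 vs 0.177 | 0.153 vs 0.143 |

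The gain survives in small arms, slightly reduced by the cost of estimating the extra slopes.

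**3. Chance baseline difference d.** Under randomisation, a chance gap d before report-back predicts a gap of rho·d afterwards. The change score then has conditional error rho·d − d = −(1−rho)d. ANCOVA subtracts rho·d and has error rho·d − rho·d = 0. Simulated slopes of the estimate on d were about −0.67, −0.48 and −0.27 for the change score (rho 0.3, 0.5, 0.7) and 0.00 to 0.02 for ANCOVA.

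**4. Systematic gap d that persists to the post-survey.** The change score has error d − d = 0. ANCOVA has error d − rho·d = (1−rho)d. The ordering reverses.

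**The case against.** The strongest reply is that nothing is broken. Under randomisation the interaction is unbiased, and the choice lies between two accepted analyses. The mixed model also gives the change within each arm, which the plan sets out to describe, and it can keep unpaired responses arising from the don't-know and decline options. Plain ANCOVA does neither directly. All of this stands, and it is why the stated model should be kept alongside.

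The size of the gain also rests on an unknown correlation. Self-efficacy is a seven-item sum and knowledge a 9- or 11-item index, so rho could be high for those outcomes, and at 0.9 the saving is only 5%. The full instruments are in a supplement, so the document cannot settle rho. That stands too.

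A reader might infer that any baseline imbalance passes in full into the stated contrast, or that ANCOVA is always the safer choice when arms differ at baseline. The documents do not support either reading. For chance imbalance the error is the fraction (1−rho) of d, not all of it. A systematic gap is also possible here: in PROTECT, contact followed assignment and came from different staff in each arm, the analysis set is limited to completers who viewed their reports, and one ERGO participant was not randomised. If such a gap persisted, the change score would do better (step 4). ANCOVA does not repair selection.

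Finally, the analyses are described in the past tense, so a new model now is a post hoc addition. That calls for disclosure, but not for leaving the analysis out.

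**Conclusion.** The point holds as one of efficiency and of conditional error under chance imbalance. It is not a charge that the stated model is invalid. For complete pairs, the arm contrast is exactly the difference in mean change, adjusted for neither the pre-survey score nor cohort. Over assumed correlations of 0.3 to 0.9, baseline adjustment would cut its variance by 35% down to 5%, given equal SDs. The advantage under baseline imbalance rests on randomisation and does not extend to a persistent systematic gap. Since the pre-survey scores are already collected and no named sensitivity model uses them as a covariate, the adjusted analysis should be added.

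**What to change.** For each outcome measured in both surveys, estimate the arm contrast in one of two ways:

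- regress the post-survey score on group, pre-survey score and cohort (for the PROTECT-only items, the cohort term drops out); or
- fit a mixed model with a common baseline mean across arms (no group difference at the pre-survey) and a cohort-by-time term, which gives a similar gain and keeps unpaired responses.

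Name the chosen contrast as the arm effect. Report it beside the stated mixed model, which continues to supply the within-arm changes, and report the observed pre/post correlation so that readers can see the gain. Label the analysis as added after the stated model, with a date. Do not choose between the ANCOVA and the mixed model by AIC: one models the post scores and the other both sets of scores, so the response vectors differ and the values are not comparable.

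The cost is a paragraph in the SAP and re-running models on existing data. The downsides are a disclosed post hoc addition and, with plain ANCOVA, the loss of unpaired item responses.

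### For outcomes measured at both surveys, the cohort main effect drops out of the group-by-time estimate, so the between-arm difference in change is not adjusted for cohort

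*Combined protocol and SAP*

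**What the plan says.** The Survey Analysis section gives the main model for outcomes asked at both surveys. It "included intervention group, cohort, and survey timepoint as predictors and an interaction between survey time point and intervention group". On the random part it says "We also included a random intercept for each participant". There is no cohort-by-timepoint term. The analysis set is narrow: "All data analysis was restricted to participants who completed the pre- and post-surveys and viewed their DERBI reports".

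Outcomes asked only after report-back (feeling surprised, satisfaction, yes/no behaviour changes) are treated differently: "we used multiple regression models that included fixed effects for intervention group and cohort only (no random effect").

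On allocation, the Study design overview says "For both cohorts, participants were randomly assigned to the clinician-guided or self-guided intervention group". It also reports an exception: "One ERGO participant was prospectively assigned to the clinician-guided group". It gives no allocation ratio and no numbers per cohort and arm, and does not say in so many words that randomisation was stratified by cohort, although that is the natural reading.

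**The concern.** A reader who sees cohort in the main model will assume that the intervention effect is adjusted for it. For the post-survey-only outcomes that is true. For self-efficacy, knowledge, behaviour frequency and feelings other than surprised, it is not: the effect there is the group-by-time interaction, and a time-constant covariate does not touch it.

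This matters because change from pre to post may differ by cohort for reasons that apply to both arms. PROTECT surveys were taken by phone and ERGO surveys online. PROTECT reports covered phenolic compounds and phthalates, and ERGO reports phthalates only. If the two arms, as analysed, hold different proportions of ERGO participants, part of any such cohort difference is credited to, or taken from, the clinician.

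The arm split could come to differ by cohort. PROTECT used different staff to contact the two arms, while one coordinator contacted everyone in ERGO. PROTECT clinician-guided participants had to travel to a clinic, while those in ERGO joined by video. The analysis then keeps only people who completed both surveys and viewed their reports.

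**Working it through.** The documents state no sample size, effect size or variance, so there is no planned figure to reproduce. The core of the point is algebra; the numbers below rest on assumed inputs.

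**1. Why the cohort term cancels.** For person *i* with group G, cohort C and time t = 0 or 1, the planned model is

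y = b_i + α + βG + γC + τt + δ(G × t) + e.

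The person's change is y(1) − y(0) = τ + δG + (e₁ − e₀). Both b_i and γC are gone. With two complete visits per person, the estimate of δ is therefore

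δ̂ = mean change (clinician-guided) − mean change (self-guided),

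with or without C in the model.

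**2. What follows if change differs by cohort.** Let θ = ERGO change − PROTECT change, and let p₁ and p₀ be the ERGO shares of the analysed clinician-guided and self-guided arms. Then

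bias of δ̂ = (p₁ − p₀) × θ.

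It is zero if either factor is zero.

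**3. Numerical check.** Assumed: 80 PROTECT and 40 ERGO participants, random-intercept SD 1.0, residual SD 0.8, cohort level difference 0.8, mean change 0.6 in PROTECT and 0 in ERGO (θ = −0.6), true group-by-time effect 0.3. REML mixed models on one simulated data set per split, complete pairs, estimate (SE):

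| Split, clinician/self | No cohort term | Cohort main effect | Cohort × time |
|---|---|---|---|
| Same: PROTECT 40/40, ERGO 20/20 | 0.27492 (0.22257) | 0.27492 (0.22257) | 0.27492 (0.21614) |
| Mild imbalance: 35/45, 25/15 | 0.04351 (0.22133) | 0.04351 (0.22133) | 0.14767 (0.21916) |
| Strong imbalance: 25/55, 30/10 | −0.21455 (0.21828) | −0.21455 (0.21828) | −0.01208 (0.23652) |

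The first two columns are identical and equal the raw difference in mean change.

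**4. Bias.** Mean over 500 simulated trials, true effect 0.3:

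| Split | p₁ − p₀ | Formula bias | Mean, planned model | Mean, cohort × time |
|---|---|---|---|---|
| Same | 20/60 − 20/60 = 0 | 0 | 0.308 | 0.308 |
| Mild | 25/60 − 15/60 = 0.167 | −0.10 | 0.214 | 0.312 |
| Strong | 30/55 − 10/65 = 0.392 | −0.235 | 0.079 | 0.311 |

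**5. Precision with equal splits.** 0.21614 / 0.22257 = 0.971, so the added term lowers the SE by about 3%. Under strong imbalance the SE rises instead (0.21828 to 0.23652), which is the price of removing the bias.

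**6. Broken pairs.** On the surveys, "For each question, participants also had the option to select" Don't Know or Decline to Answer, and the handling of these answers is not stated. With 10% of responses missing at random, adding the cohort main effect moved the estimate only slightly: 0.172 to 0.188 (same), −0.113 to −0.100 (mild), −0.329 to −0.323 (strong). So the cancellation is then approximate, and the main effect still does little adjusting.

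**7. The hand-assigned participant.** Assume 50/50 in PROTECT, 21/19 in ERGO and θ = 0.5. Then p₁ − p₀ = 21/71 − 19/69 = 0.020, and the bias is 0.020 × 0.5 = 0.01.

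**The case against.** The strongest reply is that the harm needs an imbalance that the documents do not show. Participants in both cohorts were randomised. In a simulation with 100 PROTECT and 40 ERGO participants, θ = 0.5, a change SD of about 1.2 and no true effect, the planned test rejected 4.6% of the time with 1:1 allocation within cohort and 4.9% with simple 1:1 randomisation, with mean bias 0.00 in both. It rejected about 10% of the time (9.5% and 10.1% in two runs) only when the split was fixed at 60/40 in PROTECT and 10/30 in ERGO. This stands: a reader might infer that the planned test has an inflated type I error, and the documents do not support that. Nor does the one hand-assigned participant amount to a material source of bias.

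A reader might also infer that no intervention effect in the plan is adjusted for cohort. That is too broad. For the post-survey-only outcomes the group and cohort fixed effects do adjust the comparison, and the relationship questions were asked only in PROTECT.

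Third, the cohorts differ in how the clinician visit was delivered: PROTECT used study nurses in person, whereas for ERGO "clinicians (n=3) had no previous affiliation with the ERGO study", met participants by video and had a script. It is tempting to cite this in support of a cohort-by-time term. But it bears on the clinician-guided arm only, so it is a reason to expect the intervention effect itself to vary by cohort, which an additive term does not address. The 11 versus 9 knowledge items are already normalised for their number.

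Finally, the plan does report descriptive statistics and pre/post tests by cohort and arm, and it mentions alternate models without giving their terms. A cohort-by-time term in one of those cannot be ruled out. But the stratified tests compare pre with post, not arm with arm, and an unspecified sensitivity model does not change what the main model estimates.

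**Conclusion.** The point holds for outcomes measured at both surveys in both cohorts. It is exact with complete pairs, which the restriction to completers makes the normal case, and approximate where an item answer is missing. The actual bias cannot be computed: it depends on analysed numbers by cohort and arm, and on cohort-specific change, neither of which the documents give. Under the assumed inputs it runs from zero (equal splits) through −0.10 (mild imbalance) to −0.235 (strong imbalance) against a true effect of 0.3; the last two are illustrations, not estimates for this trial. With equal splits the only loss is about 3% of the SE. This should be fixed because the remedy is nearly free and the model does not do what the presence of cohort in it suggests. The documents do not show that the results are in fact biased.

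**What to change.** - Add cohort by survey timepoint to the main model: `y ~ group*time + cohort*time + (1|participant)`. With complete pairs, regressing change on group and cohort gives the same group estimate.
- Report the numbers analysed by cohort and arm, so that a reader can judge p₁ − p₀.
- Because the clinician-guided intervention was delivered differently in each cohort, report the group-by-time estimate within PROTECT and within ERGO, labelled exploratory.
- Leave the post-survey-only models as they are on this point.

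The cost is one degree of freedom and one table. No new data are needed. If the arm splits turn out to be very unequal across cohorts, the SE of the adjusted estimate will be somewhat larger.
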